This study will utilize a between group repeated measures design to measure the effects of the learned MBSR intervention over time. MBSR will be the independent variable. Dependent variables include mindfulness, diabetic quality of life and HbA1c. Adolescents with Type 1 diabetes will be randomly assigned to an intervention group or a wait list/control group that will be offered MBSR after all data has been collected. The study will utilize a 2 (experimental versus wait-list control group) by 3 (pretest [Time 1], posttest [Time 2], and 3 month follow-up [Time 3]) to examine within and between group differences overtime on two psychosocial measures including mindfulness and quality of life. The physiological measure under study, HbA1c, reflects glucose control over the previous three month period and will be measured at Time 1 and Time 3. MBSR training will be provided via an online website and secure data collection site called *MySweetMind.org*.

Instruments

Two questionnaires will be used to collect data on psychosocial measures at the three time points including: 1) Diabetes Quality of Life Measure for Youths (YDQOL) (Ingersoll & Marrero, 1991) (Appendix A) and, 2) Mindful Attention and Awareness Scale for Adolescents (MAAS-A) (Brown, 2011) (Appendix B). A researcher-generated demographic sheet (DDS) (Appendix C) will also be administered at Time 1 to describe the population. These questionnaires will be administered to the participants via a secure, online data collection site in both the experimental and control groups. In addition, HbA1c will be measured at the beginning of the study (Time 1) to measure blood glucose over the previous three month period and after three months of participation in the study (Time 3) in participants in both the experimental and control group

Diabetes Quality of Life Measure for Youths (YDQOL) (Appendix A) will be used to measure adolescents on life satisfaction, diabetes impact, worries about diabetes, school life and peers. The YDQOL has a Cronbach alpha of 0.92 (Ingersoll & Marrero 1991). The YDQOL will take approximately 15 minutes to complete.

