The population under study will include adolescents with Type 1 diabetes between the ages of 12 and 17. To participate, adolescents will need to have the ability to read English at a sixth grade level with no cognitive impairment and have access to a computer and the Internet. A power analysis was conducted using a medium effect size of 0.25, power of .80 with alpha set at .05 using a two tailed test of significance; thus, a total sample size (N) of 86 (n=43), per group will be needed.

Recruitment of Subjects

Recruitment fliers (Appendix F) will be posted at pediatric endocrinology offices in New Jersey. In addition, email invitations will be sent through the Diabetes Education and Camping Association (DECA). The primary recruitment method will be through direct promotion to parents and campers at two summer camps for adolescents with diabetes, one day camp and several other two-week/overnight camps. Information will be provided at intake and outtake days of the camp to the parents and campers. Both parents and camper will be given a postcard with the website address and general information about participating. Secondly, eleven Pediatric Endocrinology offices in New Jersey will be contacted in order to gain access to adolescent patients diagnosed with Type 1 diabetes. Physicians will be sent a letter (Appendix G) and asked to return an included post card if they are interested in having their patients participate in this study and if they are willing to help with recruitment including posting recruitment fliers and sending invitations (Appendix H) to adolescents and the parents of adolescents with Type 1 diabetes. Permission to recruit at these sites will be obtained. Additional recruitment activities will include word of mouth and announcements placed on the Internet via parent and child support groups.

Participants of this study will be able to participate in the privacy of their own home via a website for learning the MBSR program. Study participants will access the intervention through a developed website, *MySweetMind.org*. In addition, collection of all psychosocial data will occur via a secure online data collection site. HbA1c will be obtained via a self-collected finger-stick blood test at two specific time periods and the results will be sent by the participants' parents via email to the researcher for analysis.

Informed Consent Procedures

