The principles of MBSR will be divided into 6 main modules delivered in the online, web-based format via the website: *MySweetMind.org* (Appendix I). Participants will be given a password to access a 6 week module-based site to learn Mindfulness Based Stress Reduction adapted for adolescents. This adaptation of MBSR is based on the work of [name], FAAP and [name] as presented in the book (2015) written by [name], *The Mindful Teen*. The major topics included in each module are as follows: Module 1- Introduction to Mindfulness, Mindful Eating; Module 2 – Sitting Meditation; Module 3 – Body Scan; Module 4 – Mindfulness of Thinking & Everyday Mindfulness; Module 5 – Loving Kindness Meditation & Mindfulness Movement; and, Module 6 - Review & Tips for Maintaining a Mindfulness Practice. The key concepts for each module are shown in Appendix D. The website, *MySweetMind.org*, is currently under construction. The design will be user friendly, attractive and age appropriate. Each of the modules listed above will have short video vignettes (5-10 minutes) describing the content for current module. As the participant enters each module they will see images, hear music and voice descriptions which describe the mindfulness concept for that module. Also, the participant will see a written outline of the material that can easily be printed out, if the participant chooses to. In addition, suggestions for practice of the material will be given for each module. As the participant completes modules, they receive tokens representative of that completion which move forward as progress is made through the modules. The website is being designed to work on smaller devices such as phones and tablets as well as a computer.

Collection of Data and Method of Data Analysis

Upon initial access of the website, the participant will be asked to first complete the DDS, YDQOL and MAAS questionnaires delivered online and submitted online. In addition, the participants will be asked to test their HbA1c using a finger stick home testing kit that will be

sent via US mail to the parents of the adolescents who have agreed to participate. The parent of the participant will be asked to e-mail the results of the HbA1c to the PI.

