Once all Time 1 data have been obtained, the participant will begin to go through the modules learning mindfulness. Within the website, the participant will be prompted to go to the diary page where the time spent on each module and time spent practicing the concepts of it will be recorded. This diary data will be accessible to the researcher. At the end of the 6 weeks allotted for the Module progression, the participants will be asked to take the YDQOL and the MAAS-A questionnaires again online. They will be encouraged to practice the mindfulness modules for 10-15 minute daily which will continue to be available. At Time 3, the participants in both the experimental and control groups will be asked to take the YDQOL and the MAAS-A questionnaires again one last time. The HbA1c test kit will also be sent to the home again and the results of this test will be emailed to the researcher. Those randomly assigned to the control group and thus, not yet had the opportunity to learn MBSR will be asked to take the YDQOL and MAAS-A questionnaires again at Time 2 and then the YDQOL and MAAS-A along with another HbA1c at Time 3. Once all data has been collected from those participants randomly assigned to the control group, participants will be offered the MBSR intervention.

Participants will be given a \$15.00 *iTunes or Amazon* gift card for completing the first three questionnaires and the HbA1c test at Time 1. The gift card will be sent via U.S. Mail upon confirmation of the receipt of the HbA1c results and completion of the questionnaires. At the end of the study, participants will be sent via U.S. Mail an additional \$25.00 *iTunes or Amazon* gift card upon receipt of the second HbA1c test results and completed questionnaires.

Procedures for the participants randomized to the control group will follow the same procedures as noted above except that they will not have access to the MBSR learning modules until the end of the three month data collection period. Those who were placed in the control group will be provided the opportunity to access the website and utilize the modules to learn mindfulness after all data have been collected and the intervention was shown to be effective in at least one variable measured.

Planned Analysis

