Descriptive statistics will be used to describe the population under study including means, standard deviations, ranges, and percentages to summarize the information gathered on the demographic data sheet (DDS). Graphs and histograms will be generated to view demographic data and data collected on the major variables under study at Time 1 including mindfulness, diabetes quality of life and HbA1c. Assumptions for parametric testing will be tested to determine whether or not parametric testing can be done. Although parametric testing is planned, it may be that the equivalent nonparametric test will be used to analyze data. In addition, a correlational matrix will be created to determine whether any two variables co-vary at > 0.65 . Two way repeated measures Analysis of Variance (RM-ANOVA) will be used to answer the research questions.

Interactions with Subjects and Subjects' rights

In the development of this study, careful consideration was given to maintain the 7 principles as outlined within the NIH document concerning treatment of research subjects. Specific to the

interactions with subjects, a fair subject selection will be utilized, IRB approval and informed consent will be obtained. Additionally, respect for enrolled subjects will be demonstrated by checking on their well-being as they participate, maintaining confidentiality and sharing results with them once the study is complete. Those subjects who are in the control group will also be given the opportunity to learn MBSR at the completion of data gathering since it has been shown in many populations to be a benefit and advantage to individuals with varied health conditions.

All information gathered including data, parental permission/consent and assent forms will be stored in a locked cabinet with careful attention to the privacy of participants and security of all materials. The website will be accessible only through log in and is a private website; additional security was added by purchasing secure sockets layer (SSL) encryption for the website. A secure connection is created between the participant and the server which provides compliance with HIPPA regulations and confirms the security of the data. Only the researcher and advisor will have access to the data collected.

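### The planned two-way RM-ANOVA treats the pre-treatment Time 1 score as an outcome; adjusting for Time 1 gives more power from the same data, most clearly when the Time 1 to follow-up correlation is low or moderate

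*Protocol*

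**What the plan says.** The Planned Analysis section of the Protocol names one inferential method: "Two way repeated measures Analysis of Variance (RM-ANOVA) will be used to answer the research questions". Under Research Design and Procedures, mindfulness and quality of life follow a two-group design crossed "by 3 (pretest [Time 1], posttest [Time 2], and 3 month follow-up [Time 3]) to examine within and between group differences overtime", so the pretest is one of the three outcome levels. HbA1c has two waves only; it "will be measured at Time 1 and Time 3".

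Time 1 is a pre-treatment measurement. The section Collection of Data and Method of Data Analysis gives the order of events. It begins with the questionnaires: "Upon initial access of the website, the participant will be asked to first complete the DDS, YDQOL and MAAS questionnaires". The intervention comes afterwards: "Once all Time 1 data have been obtained, the participant will begin to go through the modules learning mindfulness". Participants are randomised. The Protocol nowhere adjusts for the Time 1 score or constrains the two arms to a common Time 1 mean.

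Sample Selection and Size says: "A power analysis was conducted using a medium effect size of 0.25, power of .80 with alpha set at .05", two-tailed, giving 86 in total (43 per group). It gives no correlation between time points and does not say whether the group effect or the group-by-time effect is the test.

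**The concern.** In a randomised trial the expected group difference at Time 1 is zero. A score taken before treatment says nothing about the treatment effect, but it can explain much of the variation in later scores. RM-ANOVA spends it as an outcome level: the group-by-time test in effect subtracts Time 1 in full, which adds noise unless Time 1 and follow-up are highly correlated. Regression on Time 1 uses the amount of adjustment that the data support.

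The trial is small and aims at power of 0.80. The choice of model could therefore decide whether it can detect the effect it was sized for, at no cost in participants or visits.

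**Working it through.** **Inputs.** From the Protocol: 43 per group, two-sided .05, target power 0.80, effect size 0.25. Assumed: 0.25 is Cohen's f, which for two groups is d = 2 × 0.25 = 0.5 SD; this difference applies at follow-up and is zero at Time 1; variances are equal; data are complete. The Time 1 to follow-up correlation ρ is not given, so a range is shown.

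**The Protocol's own figure.** N = 86 is reproduced as the RM-ANOVA group main effect over three times with an assumed ρ of .5. The noncentrality is f²·N·m/(1+(m−1)ρ) = 0.0625 × 86 × 3/2 = 8.06 on 1 and 84 df, and power is 0.801. This effect averages over Time 1.

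**HbA1c (two waves).** With two waves the group-by-time test is a t test on change.

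- Change: error variance 2(1−ρ), so d = 0.5/√(2(1−ρ)), 84 df.
- ANCOVA: error variance 1−ρ², so d = 0.5/√(1−ρ²), 83 df.
- Variance ratio, ANCOVA to change: (1+ρ)/2, which is below 1 for every ρ below 1.

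At ρ = .5 the change variance is 1.00 and the ANCOVA variance 0.75. Power from the noncentral t, and the n per group for 80% power:

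| ρ | Change, power | ANCOVA, power | Change, n | ANCOVA, n |
|---|---|---|---|---|
| .3 | 0.49 | 0.67 | 89 | 59 |
| .5 | 0.63 | 0.75 | 64 | 49 |
| .6 | 0.73 | 0.82 | 52 | 42 |
| .7 | 0.84 | 0.89 | 39 | 34 |
| .8 | 0.95 | 0.97 | 27 | 24 |

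ANCOVA reaches 0.80 at ρ = .575 and change at ρ = .665.

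**Questionnaires (three waves), 2 df against 2 df.** Comparing tests with equal numerator df keeps the gain from coming merely from a switch to a 1-df average. Under compound symmetry:

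- Group-by-time: F(2,168), noncentrality (43/2)·Σ(δ_t − mean δ)²/(1−ρ). For δ = (0, .5, .5) or (0, .5, 0) the sum of squares is 0.1667, so at ρ = .5 it is 21.5 × 0.1667/0.5 = 7.17.
- Adjusted for Time 1: F(2,82), noncentrality (43/2)·f′S⁻¹f, where f holds the effects at Times 2 and 3 and S is their covariance given Time 1 (diagonal 1−ρ², off-diagonal ρ−ρ²). At ρ = .5 this is 10.75 for equal effects and 8.06 for an effect at one time only.

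| ρ | Equal effect: interaction | Equal effect: adjusted | One time only: interaction | One time only: adjusted |
|---|---|---|---|---|
| .3 | 0.51 | 0.78 | 0.51 | 0.59 |
| .5 | 0.66 | 0.83 | 0.66 | 0.70 |
| .7 | 0.88 | 0.94 | 0.88 | 0.89 |
| .8 | 0.97 | 0.985 | 0.972 | 0.974 |

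**Without compound symmetry.** Simulation, 8,000 trials per case, correlations .7 (Times 1–2), .7 (Times 2–3) and .49 (Times 1–3), epsilon .875. Greenhouse-Geisser corrected RM-ANOVA against the 2-df adjusted test gave 0.75 against 0.85 (equal effects), 0.84 against 0.94 (Time 2 only) and 0.75 against 0.81 (Time 3 only). Null rejection was .056 for uncorrected RM-ANOVA, .049 corrected and .048 adjusted.

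**If the group main effect is the intended test.** A 0.5 SD effect at Times 2 and 3 averages over three times to (0 + 0.5 + 0.5)/3 = 0.33 SD. Main-effect power at 86 is then 0.55, 0.47 and 0.40 at ρ = .3, .5 and .7. ANCOVA on the mean of Times 2 and 3 has 0.87, 0.90 and 0.97. Against this test the gain grows with ρ.

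**The case against.** The strongest reply is that nothing here is wrong. The design and analysis sections agree, the group-by-time test is valid, and covariates and contrasts are often left to a SAP that is not shown. The validity point stands: this is an efficiency gain, not an error. The SAP point does not, because the Protocol itself fixes RM-ANOVA as the method that answers the research questions.

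Other points stand in part:

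- The statement that the gain is largest at low or moderate correlation holds against the group-by-time test only. Against the group main effect the pattern reverses, although adjustment still wins at every correlation computed.
- The gain can be negligible. For a questionnaire effect at one time only it is 0.2 points at ρ = .8, and at ρ = .9 with an effect of 0.3 SD both tests have power 0.900.
- The Protocol does not say that Time 1 is completed before the arm is known. Suppose that knowing the arm shifts Time 1 answers by s. If later answers do not shift, change is biased by s and ANCOVA by ρs. If the shift persists unchanged, change is unbiased and ANCOVA is biased by (1−ρ)s. Neither method is safe in both cases, so this is a reason to settle the order of events rather than to keep RM-ANOVA.
- A model of Times 2 and 3 does not directly test change within a group, which the design section mentions. That change can be reported descriptively; the research questions are comparisons with the control group.

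**Conclusion.** The concern holds as an improvement that should be made. For HbA1c at 43 per group and 0.5 SD, ANCOVA gains 18 points of power at ρ = .3 and 12 at .5, with both tests below 0.80. The choice moves power across 0.80 only for ρ of about .58 to .66. Above that both tests reach the target, and the gain is 5 points at .7 and under 2 at .8. For the questionnaires under compound symmetry, the 2-df gain runs from 27 points (equal effects, ρ = .3) down to almost nothing (one time only, ρ = .8).

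The direction for HbA1c follows from the variance formulas and does not depend on the effect size. The sizes rest on reading 0.25 as Cohen's f, on the assumed correlations, on complete data and, for the tabulated questionnaire powers, on compound symmetry. The comparison takes the group-by-time effect as the RM-ANOVA test.

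**What to change.** Replace the RM-ANOVA sentence in Planned Analysis with:

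- **HbA1c:** ANCOVA of the Time 3 value on group and the Time 1 value.
- **MAAS-A and YDQOL:** a mixed model of the Time 2 and Time 3 scores on group, time, group-by-time and the Time 1 score. Name the treatment contrast in advance: the joint 2-df group effect, one time point, or the average of the two.

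State whether Time 1 is completed before the participant learns the arm. If RM-ANOVA is kept for the questionnaires, say which effect is the test and which sphericity correction applies.

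The cost is a change of wording and one error degree of freedom for the Time 1 covariate. It needs no further participants, visits or data and runs in standard software. It should be fixed before outcome data are seen.

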Appendix G

Sample Pediatric Endocrinologist Recruitment Letter

April 1, 2015

[name]
Pediatric Endocrinology

Dear [name],

This letter is to request the participation of your office in research concerning the use of Mindfulness as a stress management technique for adolescents with Type 1 diabetes.

I am conducting this study as partial fulfillment of the requirements for the PhD degree in Nursing at Duquesne University. IRB approval to conduct this study has been obtained through Duquesne University.

I am asking for your help to recruit adolescents between the ages of 12 to 17 with Type 1 diabetes to participate in this study. Participants will be randomized to the experimental group or the waitlist/control group. If interested, the participants will be invited to learn the practice of mindfulness via modules on a website, asked to practice the MBSR techniques, and asked to respond to questionnaires via a secure online data collection site. The home page of the website where your patient will access the course material is www.mysweetmind.org.

If you agree to help me recruit, business cards and postcards will be provided to you to give to your patients and their parents that will contain information about the study. If your patients are interested, they will be asked to contact me directly. Participants would be under no obligation to join the study or continue in the study once they join.

Please complete and send via U.S. Mail the enclosed pre-stamped postcard if you permit this study to be advertised in your office. I am available to meet with you and/or your staff directly to describe the study further or answer any questions you may have.

I encourage you to consider this opportunity for your patients. Mindfulness has become quite popular in the last few years and has shown significant benefits for many different individuals with varying conditions/illnesses. The skills that your patient could gain have the potential for helping them for a lifetime.

Please do not hesitate to contact me with any questions. My cell phone number is [contact]

Sincerely,

[name], MSN, RN, CNE
PhD Candidate
Duquesne University
School of Nursing

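### Two-way RM-ANOVA in its standard form drops any adolescent with a missing wave from the mindfulness and quality-of-life analyses, which costs power and can bias the comparison if dropout relates to response

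*Protocol*

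**What the plan says.** Under Planned Analysis, the protocol fixes one method: "Two way repeated measures Analysis of Variance (RM-ANOVA) will be used to answer the research questions". The only alternative it names is that "it may be that the equivalent nonparametric test will be used to analyze data". That alternative depends on checks of parametric assumptions, not on missing data.

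Under Research Design and Procedures, mindfulness and quality of life form a two-group by three-time design, "pretest [Time 1], posttest [Time 2], and 3 month follow-up [Time 3]". HbA1c "reflects glucose control over the previous three month period and will be measured at Time 1 and Time 3", so it has two waves.

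Under Sample Selection and Size, "A power analysis was conducted using a medium effect size of 0.25", with "power of .80 with alpha set at .05", two-tailed; "thus, a total sample size (N) of 86 (n=43), per group will be needed". No dropout rate or inflation is given, nor is the correlation between waves or the effect being tested (group, or group by time).

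The model recruitment letter in Appendix G tells physicians: "Participants would be under no obligation to join the study or continue in the study once they join".

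**The concern.** Standard RM-ANOVA needs a complete set of scores from each participant. In the two three-wave analyses, an adolescent with Time 1 and Time 3 but no Time 2 is removed whole, and so is one with Time 1 and Time 2 but no Time 3. Data come from home over about three months, by self-completed online questionnaires, and participants may stop, so some incomplete sets are likely.

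Two things are at stake. First, usable scores are discarded, and power falls in a trial sized with no stated reserve. Second, those left are a subset formed after randomisation. If MBSR participants who see little early benefit leave more often, the completers in that arm are selected for benefit, and the comparison is no longer between the groups as randomised.

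**Working it through.** **1. Reproducing N = 86.** Inputs from the protocol: f = 0.25, alpha 0.05, two groups, m = 3 waves. Assumed: correlation between waves ρ = 0.5. For the between-group effect, λ = f²·N·m / (1 + (m − 1)ρ), with 1 and N − 2 degrees of freedom. At N = 86, λ = 0.0625 × 86 × 3 / 2 = 8.06 and power is 0.801. This is the smallest even N to reach 0.80. With ρ from 0.3 to 0.7 the same formula asks for 70 to 104. Other readings do not give 86: the group-by-time effect at f = 0.25 gives 28, and one-way ANOVA gives 128. So 86 matches a requirement for complete data from everyone.

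**2. Deleting incomplete sets, same test.** The dropout rates are assumed.

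| Incomplete | Analysed | λ | Power |
|---|---|---|---|
| 0% | 86 | 8.06 | 0.801 |
| 10% | 77 | 7.22 | 0.756 |
| 20% | 68 | 6.38 | 0.701 |
| 30% | 60 | 5.63 | 0.645 |

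**3. What a model using all scores recovers.** This uses the group-by-time test. Assumed: a true difference d = 0.5 SD at Times 2 and 3, none at Time 1, equal correlations, and missingness completely at random. For n complete participants per arm, λ = n·d² / (3(1 − ρ)), with 2 and 2(N − 2) degrees of freedom. Full data at ρ = 0.5: 43 × 0.25 / 1.5 = 7.17. For all available scores, the information from each missingness pattern is summed, V = 2 × (summed information per arm)⁻¹, and λ = δ′(CVC′)⁻¹δ. Here C forms the two changes from Time 1, δ = (0.5, 0.5), and the denominator degrees of freedom are scores minus participants minus 4.

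| Pattern | ρ | Completers: λ, power | All scores: λ, power |
|---|---|---|---|
| Full data | 0.5 | 7.17, 0.66 | same |
| Full data | 0.6 | 8.96, 0.76 | same |
| 20% missing independently at each follow-up (64% complete) | 0.5 | 4.59, 0.46 | 6.43, 0.61 |
| as above | 0.6 | 5.73, 0.55 | 8.00, 0.71 |
| Monotone: 10% gone by Time 2, 20% by Time 3 | 0.5 | 5.73, 0.55 | 6.50, 0.61 |
| as above | 0.6 | 7.17, 0.66 | 8.06, 0.71 |
| All 20% gone before Time 2 | 0.5 | 5.73, 0.55 | 6.14, 0.58 |
| as above | 0.6 | 7.17, 0.66 | 7.57, 0.68 |

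The gain is about 15 to 16 points in the intermittent pattern, about 6 under monotone dropout, and about 3 if everyone who leaves does so before Time 2. A simulation of the intermittent pattern (1,000 trials per cell) gave 0.454 against 0.578 at ρ = 0.5 and 0.555 against 0.710 at ρ = 0.6, so 12 to 16 points covers both methods.

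**4. Bias.** With missingness completely at random, a simulation with 10% missing Time 2 and 20% missing Time 3 showed none: the completers' wave-averaged difference was 0.32 against a true 0.33 SD.

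Now take no true effect, MBSR dropout before Time 3 driven by poor Time 1 to Time 2 change (logistic slope −1.5 per SD), and control dropout at the same rate but unrelated to response. All of this is assumed. At ρ = 0.5 and 10%, 20% and 30% dropout, retained MBSR participants have baseline means shifted by about −0.06, −0.11 and −0.16 SD and Time 2 means by about +0.06, +0.11 and +0.16. Their Time 3 means stay at about zero. The spurious change from baseline is therefore 0.12, 0.23 and 0.33 SD at Time 2, and 0.06, 0.11 and 0.16 to 0.17 SD at Time 3. At ρ = 0.6 the values are 0.10, 0.19 and 0.28, and 0.05, 0.09 and 0.14. The mixed-model estimate at Time 3 was within 0.005 of zero.

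A different mechanism gives a different picture. If MBSR participants leave because of a poor Time 2 score, and the true Time 3 difference is 0.50 SD, completers show a Time 3 level difference of 0.61 to 0.66. Their Time 1 to Time 3 change is almost unbiased (0.50 to 0.52).

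**The case against.** **Deletion is not written down.** It is a property of the named method in its usual form. No sentence defines a completers-only set, and an SAP that was not available for this review could impute before RM-ANOVA. That stands as a limit on certainty. It does not remove the point, because the protocol names the method and its only stated alternative does not address missing data.

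**A reader might infer that the plan does bias the result.** The documents do not support that. They give no evidence that leaving relates to response, and bias is absent under completely random missingness. Nor do they show that incomplete sets are certain: Appendix G says only that participation is voluntary. The protocol also plans text, e-mail and website reminders and a $25 gift card at the end.

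**A reader might take the 0.05 to 0.17 SD at Time 3 as a false difference between groups at that visit.** It is a change-from-baseline contrast. The level difference at Time 3 is about zero in that scenario, and at Time 2 it is about half the change contrast. The change contrast still matters, because a group-by-time test uses it.

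**The power gain depends on the pattern.** This stands: it can be as little as 3 points, and much of the loss comes from the missing data itself.

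**The shortfall depends on the effect tested.** If f = 0.25 were meant for the group-by-time effect, power would remain 0.98 even at 40% incomplete (ρ = 0.5). That reading does not reproduce 86. It also implies λ = 0.0625 × 86 × 3 / 0.5 = 32.25, which corresponds to a sustained difference of about 1.06 SD (√(32.25 × 1.5 / 43)).

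**Follow-up of those who stop the modules is already implied.** Collection of Data and Method of Data Analysis asks both groups for Time 3 data without tying this to module completion. So this part needs only to be made explicit.

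**Conclusion.** The point holds for MAAS-A and YDQOL. In its standard form the named method discards the partial data of anyone without all three scores, in a trial whose size matches a complete-data requirement and has no stated dropout allowance. On the test that reproduces 86, power falls from 0.80 to about 0.76, 0.70 and 0.65 at 10%, 20% and 30% incomplete. For the group-by-time test with an assumed 0.5 SD effect, using all scores recovers about 6 points under monotone dropout and about 12 to 16 under independent 20% losses.

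Bias is possible, not established. Its size and even the contrast affected depend on why participants leave. For HbA1c only a missing Time 1 or Time 3 value matters. Correlations of 0.5 to 0.6, all dropout rates and all mechanisms are assumptions, because the protocol gives none.

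**What to change.** In Planned Analysis, replace RM-ANOVA for MAAS-A and YDQOL with a likelihood-based linear mixed model for repeated measures (group, time, group by time). Include every randomised participant with any score, in the group assigned. Report the completers-only RM-ANOVA as a sensitivity analysis. In Collection of Data and Method of Data Analysis, say outright that Time 2 and Time 3 measurements are requested whether or not the modules were completed.

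The cost is about a paragraph of text and standard software, with no added participants or visits. The small downside is that the mixed model assumes missingness is explained by observed scores; the completer analysis needs a stronger assumption. The change recovers part of the lost power, not all of it.
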